## 6.3. Study period and important time points.

The study period is June 2018-June 2019.

The index date for the cases is defined as the date of the stool sample collection (either June/July 2018 or Oct/Nov 2019).

The index date for the controls is defined as the date of the stool sample collection either June/July 2018 or Oct/Nov 2019).

Queries within the CRF relate to that patients episode, with reference to the six months prior and six months subsequent to the index sample.

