#### 3.2.6 Data collection

Data will be collected via a standardised CRF, with a full supporting SOP. The CRF will be completed by the clinical care team at the participating site that submitted the sample (during O1.1). The CRF will not contain any participant identifiable data; all data will be held against a pseudoanonymised study code, with the link back held by the clinical care team only. COMBACTE-CDI investigators will not access participant's notes or access the link back. Once the CRF data has been collected and validated and verified the link-back will be destroyed by the local study site.

Data will be collected on the following variables on outcomes of CDI;

- Evidence of other enteric pathogens (+/- 7 days of the original sample)?
- Symptoms at time of the sample
- Alternative cause for the patient's diarrhoea documented (e.g. laxatives, pathogen)?
- Duration of diarrhoea/non-normal bowel habit?
- Primary/recurrent CDI
- Antibiotics at the time of the sample or the preceding 3 months?
- Evidence of colitis?
- Evidence of post-infectious diarrhoea

- CDI Severity markers (Temperature (nearest reading +/- 3 days of the sample), serum creatinine (nearest reading +/- 3 days of the sample), White cell count (nearest test +/- 3 days of the sample)
- Treatment for CDI episode
- Was treatment for CDI/diarrhoea escalated medical/surgical?
- Outcome 30 days and 6 months after the sample (discharged, in-patient, died)
- Length of stay

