	symptoms at time			was taken
	of index sample			
5.9	Was there an	Binary	Univariate	Patient admission
	alternative cause			when the sample
	for the patients			was taken
	diarrhoea			
5.9.1	If yes please give	Categorical	Univariate	Patient admission
	details			when the sample
				was taken
5.10	Duration of	Number of	Univariate	Patient admission
	diarrhoea before	days of		when the sample
	and after the index	diarrhoea is		was taken
F 44	sample	Continuous		Detionst e destade
5.11	Did the patient	віпагу	Univariate	Patient admission
	undergo any			when the sample
	diagnostic			was taken
	procedures for this			
	episode of CDI?			
5.11.1	It yes, please	Categorical	Univariate	Patient admission
	complete the table			when the sample

				was taken
5.12	Evidence of colitis	Binary	Univariate	Patient admission
				when the sample
				was taken
5.12.1	If yes please give	Categorical	Univariate	Patient admission
	details			when the sample
				was taken
5.13	Was the patient in	Binary	Univariate	Patient admission
	contact with a			when the sample
	diagnosed			was taken
	Clostridium difficile			
	case in the			
	preceding 3 months			
E 12 1		Catagorical	Univariato	Dationt admission
5.15.1	the date	Categorical	Univariate	when the sample
				was taken
5.14	Was the patient in	Binary	Univariate	Patient admission
	kissing contact of	Dinidi y	omratice	when the sample
	an infant in the			was taken
	preceding 3 months			
	to the sample?			
5.14.1	If yes please give	Categorical	Univariate	Patient admission
	the date			when the sample
				was taken
5.15	Did the patient	Binary	Univariate	Patient admission
	receive mechanical			when the sample
	ventilation			was taken
5.15.1	If yes, please give	Continuous	Univariate	Patient admission
	une duration of the			when the sample
	minutes			was taken
5.16	Was the patient	Binary	Univariate	Patient admission
	source isolated due			when the sample
	to CDI			was taken
5.16.1	If yes, please give	Continuous	Univariate	Patient admission
	the duration of			when the sample
	source isolation in			was taken
	days			
5.16.2	Did the patient in	Binary	Univariate	Patient admission
	source isolation			when the sample
	lead to the blocking			was taken
- 10 -	of beds			
5.16.3	If yes, how many	Continuous	Univariate	Patient admission
	beas were blocked			when the sample
6 Dave 11	uuring that time?			was taken
6. Drug H	istory			

6.1	Was the patient prescribed	Binary	Univariate/multivariate	Patient admission when the sample was taken

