	at the time or after			was taken
6.1.1	If Yes please complete table	Class of antibiotic is Categorical	Univariate/multivariate	Patient admission when the sample was taken
		Number of dates of		
		Continuous	Univariate/multivariate	
		Indication is Categorical	Univariate/multivariate	
		Route is Categorical		
6.2	Was the patient prescribed antibiotics for an infection other than CDI (or for prophylaxis) in the 12 weeks preceding the index sample	Binary	Univariate/multivariate	Up to 12 weeks previous to the sample
6.2.1	If Yes please complete table	Class of antibiotic is Categorical	Univariate/multivariate	Up to 12 weeks previous to the sample
		Number of	Univariate/multivariate	
		treatment is Continuous	Univariate/multivariate	
		Indication is	Univariate/multivariate	
		Categorical		
		Route is Categorical		
6.3	Did the patient have proton pump inhibitors in the 12 weeks preceding the index sample	Binary	Univariate/multivariate	Up to 12 weeks previous to the sample
6.3.1	If yes please	Name of PPI	Univariate/multivariate	Up to 12 weeks

r				
	complete the table	is Categorical	Univariate/multivariate	previous to the sample
		Number of dates of	Univariate/multivariate	
		Continuous	Univariate/multivariate	
		Indication is Categorical		
		Route is Categorical		
6.4	Has the patient had any drugs which affect the gastrointestinal tract in the 12 weeks preceding the index sample	Binary	Univariate/multivariate	Up to 12 weeks previous to the sample
6.4.1	If yes please complete the table	Name of drug is Categorical	Univariate/multivariate Univariate/multivariate	Up to 12 weeks previous to the sample
		Number of dates of treatment is Continuous	Univariate/multivariate Univariate/multivariate	
		Indication is Categorical		
		Categorical		
6.5	Has the patient had systemic steroids or other systemic immunosuppressive drugs in the 12 weeks preceding the index sample	Binary	Univariate/multivariate	Up to 12 weeks previous to the sample
6.5.1	If yes please complete the table	Name of drug is Categorical	Univariate/multivariate Univariate/multivariate	Up to 12 weeks previous to the sample
		Number of dates of	Univariate/multivariate	

		treatment is		
		Continuous	Univariate/multivariate	
		Indication is		
		Categorical		
		Route is		
		Categorical		
7. CDI trea	Did the nation	Binary	Univariate/multivariate	Patient admission
/.1	require	Dinary		when the sample
	change/escalation			was taken
	of CDI medication			

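### Risk-factor windows run up to the stool sample, and no rule removes gut drugs, PPIs or GI procedures prompted by the diarrhoea that led to it

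*SAP*

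**What the plan says.** SAP section 6.3 fixes the anchor for both groups. For cases: "The index date for the cases is defined as the date of the stool sample collection". For controls: "The index date for the controls is defined as the date of the stool sample collection". It adds that the CRF questions are framed "with reference to the six months prior and six months subsequent to the index sample".

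SAP Appendix 1 then sets the look-back for each exposure:

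- Item 6.2: "Was the patient prescribed antibiotics for an infection other than CDI (or for prophylaxis) in the 12 weeks preceding the index sample"
- Item 6.3: "Did the patient have proton pump inhibitors in the 12 weeks preceding the index sample"
- Item 6.4: "Has the patient had any drugs which affect the gastrointestinal tract in the 12 weeks preceding the index sample"
- Items 6.5 (steroids and immunosuppressants), 8.1 (surgery) and 9.1 (GI interventions or diagnoses) use the same 12 weeks. Item 2.6 (healthcare contact) uses six months.

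SAP section 6.2 lists the drugs and procedures as potential risk factors. SAP section 7.3 offers them to a forward-selection logistic model and uses the order of entry to rank them.

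The plan does collect information on symptom timing. Appendix 1 item 5.10 asks about the duration of "diarrhoea before" and after the index sample, and Protocol 3.2.6 lists "Duration of diarrhoea/non-normal bowel habit". Item 5.10 is marked univariate and is not used to set any window. Indication is recorded for each drug group, but no rule uses it. The only sensitivity analysis named, in SAP section 5, concerns missing data.

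**The concern.** By SAP section 6.1 the outcome is a positive diarrhoeal sample, so symptoms come before the index date. Between onset and sample a patient may be given a gut-acting drug or a PPI, or may have the bowel investigated, because of the symptoms. Each of these is coded as an exposure in the weeks before the index sample and so as a candidate cause. Item 9.1 is especially open to this, because it counts GI diagnoses as well as interventions and work-up of the episode itself can qualify.

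The risk-factor objective is at stake. Protocol 3.3.1 sets out to find modifiable factors other than antibiotics and notes doubt about whether PPIs are truly associated with CDI. SAP section 2.5 compares risk factors by case classification, country and setting. If the delay from onset to sample, or the prescribing during it, differs between ward and general-practice patients, the odds ratios can differ between settings for that reason alone.

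**Working it through.** No figure in the documents depends on this window, so there is none to reproduce. The check has two parts.

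**1. Do the safeguards close the gap?**

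| Possible safeguard | What the SAP has | Effect |
|---|---|---|
| Exclusion by indication | Item 6.2 leaves out antibiotics for CDI | None for items 6.3, 6.4 or 9.1 |
| Indication recorded | Items 6.2.1 to 6.5.1 | Collected, but no rule uses it |
| Timing recorded | Items 8.1.2 and 9.1.1 give days between event and sample | Usable for surgery and GI interventions; the drug items list only the amount of treatment, and item 2.6 has no timing variable |
| Onset | Item 5.10 | Sets no window |
| Same anchor in controls | SAP section 6.3; Protocol 3.1.3.1 admits unformed stool only | Exposes both groups to the problem but does not remove it |

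The gap is therefore open for items 6.3, 6.4 and 9.1, and partly open for antibiotics.

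**2. What could it do to an odds ratio?**

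Inputs from the SAP: 213 cases and 512 controls (section 2.1); previous surgery 26% v 16% and antibiotics 67% v 45% (section 3), borrowed only as plausible exposure levels; type I error 5% (section 3), taken as two-sided because the SAP does not say. Assumed, because the documents do not give it: the share r of previously unexposed patients who start between onset and sample, 5% to 20%.

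Observed exposure = p + (1 − p) × r, where p is true pre-onset exposure. The odds ratio is the odds of this in cases divided by the odds in controls.

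*No true association, p = 0.16 in both groups.* With r = 15% in cases and 5% in controls:

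- cases 0.16 + 0.84 × 0.15 = 0.286, odds 0.401
- controls 0.16 + 0.84 × 0.05 = 0.202, odds 0.253
- odds ratio 0.401 / 0.253 = 1.58

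For the chance of p < 0.05 with 213 v 512, the difference is 0.084, the standard error under the null 0.0341 and under the alternative 0.0357. Then (0.084 − 1.96 × 0.0341) / 0.0357 = 0.48, which gives 68%.

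| r cases / r controls | Observed odds ratio | Chance of p < 0.05 |
|---|---|---|
| 5% / 5% | 1.00 | 5% |
| 10% / 5% | 1.28 | 25% |
| 15% / 5% | 1.58 | 68% |
| 5% / 15% | 0.63 | 66% |

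With p = 0.45, 15% v 5% gives 1.25 (27%), so the effect shrinks as true exposure becomes more common. If starts were equal in one setting and 15% v 5% in the other, with p = 0.16, odds ratios of 1.00 and 1.58 would suggest a setting difference that does not exist.

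*True association, equal starts in both groups.*

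| True exposure, cases / controls | True odds ratio | r = 5% | r = 10% | r = 20% |
|---|---|---|---|---|
| 26% / 16% | 1.84 | 1.67 | 1.55 | 1.41 |
| 67% / 45% | 2.48 | 2.40 | 2.32 | 2.19 |

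*Share of the window affected.* A gap of 1, 3, 7 or 14 days is 1/84, 3/84, 7/84 or 14/84 of the 12 weeks: 1.2%, 3.6%, 8.3% or 16.7%.

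**The case against.** The strongest reply is that controls also had diarrhoea, come from the same site and setting, and have the same index date. Symptom-driven prescribing then occurs in both groups, and if it is equal no false association arises. This stands, and it rules out any claim that the plan inflates its odds ratios. It does not make the windows harmless, because equal starts still dilute a true effect and nothing in the documents shows that starts are equal. Controls' diarrhoea has other causes, so delay and treatment may differ.

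A reader might go further and infer that diarrhoea onset should replace the sample date as the reference for all exposures. The documents do not support that, for four reasons:

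- Appendix 1 lists no interval from drug start to sample.
- Item 5.10 may not hold pre-sample days separately, since it is listed as one item covering before and after.
- Cutting a 12-week window at onset makes its length depend on the delay. A patient with 21 days of diarrhoea would keep 84 − 21 = 63 days.
- An antibiotic given for some other diarrhoea can be a true antecedent of CDI, and an onset cut would delete it.

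It could also be said that SAP section 7.3 admits every univariate variable to the regression, so item 5.10 might enter as a covariate. Adjusting for duration would not reclassify an exposure that began after onset.

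**Conclusion.** The concern holds in limited form. The windows end at the sample, symptoms precede it, and no rule separates exposures that came before the diarrhoea from those prompted by it. This is clearest for gut-acting drugs, PPIs and GI interventions or diagnoses. It is narrower for antibiotics, where treatment for CDI is already left out, and least plausible for elective surgery.

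Direction and size cannot be determined from the documents, which give neither the onset-to-sample delay nor start rates within it. The odds ratios above illustrate assumed rates and do not estimate bias in this study. The chances of significance use all 213 cases and 512 controls; analyses by case classification, setting or age group have fewer patients. The change is worth making because it bears directly on the risk-factor objective and mostly uses items already listed.

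**What to change.** Keep the stool date as the index date and for follow-up. Add to SAP sections 6.3 and 7, for cases and controls alike:

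1. **Main risk-factor analysis.** Do not count as exposure an item 6.3 or 6.4 drug whose recorded indication is the current diarrhoea. Do not count an item 9.1 intervention or diagnosis that falls within the days of diarrhoea before the sample (item 9.1.1 against item 5.10).
2. **Sensitivity analysis on onset.** End the windows at the sample date minus the pre-sample days in item 5.10, with one fixed look-back length for everyone. For example, 84 − 14 = 70 days fits within the 12 weeks collected for any gap up to 14 days. Limit it to patients with a recorded onset and to exposures whose timing the CRF allows.
3. **Antibiotics (item 6.2).** Exclude courses given for the current diarrhoea only as a sensitivity analysis.

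First confirm on the CRF that item 5.10 separates days before from days after the sample. If it holds only a total, the timing rule in step 1 and all of step 2 cannot be run, and the indication rules remain.

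The cost is SAP wording, derived variables and analysis time, with no new data item. The downside is that onset or drug timing will be missing for some patients, and the look-back in the sensitivity analysis is somewhat shorter.

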## 7. Statistical methodology and statistical analysis

#### 7.1 Descriptive analysis

Distribution of demographic, concomitant pathogens, medical conditions, medical procedures, and medication used will be tabulated by case and controls. The analysis will also be stratified by age group (<18, 18-49 years, 50+ 50-64 years, 65 +, 65--84 years, and 85 + years).

Where data are continuous variables, means and standard deviations will be presented; where these data have a highly skewed distribution, medians, 25th and 75th percentiles will be presented. Where data are categorical variables, the number and percentage of participants within each category will be presented. The percentage of missing values will be reported for each variable (continuous or categorical).

#### 7.2 Univariate analysis

Univariate analysis will be used to assess outcomes and risk factors; continuous variables will be compared between cases and controls by t-test; categorical variables will be compared between cases and controls by chi-squared (fishers exact where numbers are below 5). Risk ratios (Odds ratio if it is case control study) will be calculated for CDI cases with identified variables of interest. Univariate analysis will be used to assess consistency between countries and between different healthcare settings.

The variables to be included in the univariate analysis are shown in the table in appendix 1.

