#### 3.2.2 Outcome measures

Primary outcome measure: Crude mortality at 30 days and 6 months after the sample was taken will be compared between case and controls, those that received a correct diagnosis at the original hospital and those that were 'missed' (either due to lack of testing or inadequate testing) and between community and hospitalised patients.

Secondary outcome measures: Patient length of stay, severity of infection (e.g. WCC, serum albumin, temperature), need for escalation of medical/surgical care due to gastrointestinal disease, post-infectious sequelae.

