#### 3.2.7 Data analysis

Comparisons will be made between recurrence/Morbidity/Mortality (crude and attributable) rates in different healthcare settings and countries. Outcomes will also be compared for different strain types (as identified in O1.2).

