We will aim to elucidate the overall costs in all healthcare settings. Data will be compared on the costs of CDI in different healthcare settings, and to address knowledge gaps regarding managing CDI outside hospitals, including in nursing homes. For the most comprehensive analyses on overall costs associated with CDI, a micro-costing approach will be combined with published data of the respective health systems for all health-economic evaluations. Additionally, by using data from Objective 1.3, indirect costs, i.e. productivity losses due to illness related disability and death before retirement age, in inpatient and outpatient settings will be addressed from societal perspectives to measure the full impact of CDI. The human capital and/or friction cost approaches will be used. All calculated costs will be expressed in an appropriate currency (e.g. EURO, €). Furthermore, discounting of all calculated costs will be performed by taking account of country and annual discount rates (normally 3% - 5% per year). Multivariate analyses will be performed to estimate relevant components of cost. Sensitivity analyses will be performed by using different annual discount rates.

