Appendix 1. Variable description table

## 1. Introduction

This statistical analysis plan (SAP) is to provide a description of the study design, study variables, and statistical analysis methods for the COMBACTE-CDI study, which aims to develop a detailed understanding of the epidemiology and clinical impact of CDI. More specifically, this project's objectives are to:

- Align and understand the unmet public health needs relating to CDI;
- Identify and quantify the direct and long-term burden of CDI on healthcare systems

The COMBACTE CDI case/control studyfollows a cohort of patients identified during the COMBACTE CDI sample collection study. The sample collection study involved 119 sites from 12 countries from Europe, with a national coordinator recruited for every country. National coordinators selected participating sites (PS) to cover all major geographical regions within every country. Participating sites were recruited at a rate of one per 3 million population in all study countries. Figure 1 shows the full study design.

Figure 1. Schematic representation of study design (WP1 &WP2). A synergistic approach will enable completion of all the objectives from WP1 and WP2, with data created from a single, large complex study flowing into other objectives for further results analysis. Boxes in blue denote objectives in WP1, and those in orange denote for objectives in WP2. Due to the inter-related nature of the

objectives within both WP1 and WP2, the flow of work has been planned to ensure maximum outputs within the timeframe of the grant. The directions of the arrows indicates data flow and, therefore, also the timing of activities; i.e. Strains cannot be analysed (1.2) until after they have been collected (1.1). This ambitious comprehensive project design takes influence from several existing, separate studies; the scope of producing all of these is data from one, well-designed and far-reaching study is novel and innovative.

During the COMBACTE-CDI sample collection study, cases and controls were identified; Multiple diagnostic definitions of a case;

- Case defined as C. difficile toxin positive (gold standard method CCNA) positive
- Case defined as C. difficile toxin positive (new novel method –SIMOA)
- Case defined as free toxin negative but positive for a cytotoxigenic strain (by culture or detection of toxin gene)
- Control defined as negative by all assays

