#### 2.5. Analysis objectives

The main objectives of the analyses are to;

- 1. Determine the outcomes of cases (of each classification) vs controls, and compare between countries and hospital vs community cases
- 2. Determine the risk factors for cases (of each classification) vs controls, and compare between countries and hospital vs community cases

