#### 3. Sample size

Based on a previous risk factor study using a similar study design (ORCHID) the following power calculations were made;

Age >65; previously found 65% in cases and 39% in controls. Comparing proportions for equivalence, a sample size of 20 cases and 60 controls would give 80% power to detect a difference of 23% between cases and controls with an  $\alpha$  type one error rate of 5%.

At least one antibiotic; previously found 67% in cases and 45% in controls. Comparing proportions for equivalence, a sample size of 23 cases and 67 controls would give and 80% to detect a difference of 22% between cases and controls with an  $\alpha$  type one error rate of 5%.

At least one antibiotic; alternative single centre cohort found 85% in cases and 75% in controls. Comparing proportions for equivalence, a sample size of 92 cases and 276 controls would give and 80% to detect a difference of 13% between cases and controls with an  $\alpha$  type one error rate of 5%.

Previous surgery; previously found 26% in cases and 16% in controls. Comparing proportions for equivalence, a sample size of 156 cases and 469 controls would give and 80% to detect a difference of 10% between cases and controls with an  $\alpha$  type one error rate of 5%.

Previous surgery; alternative single centre cohort previously found 41% in cases and 28% in controls. Comparing proportions for equivalence, a sample size of 88 cases and 351controls would give and 80% to detect a difference of 13% between cases and controls with an  $\alpha$  type one error rate of 5%.

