#### 4. Study Design

This is case-control study with the cases and controls selected from the patients who had stool samples tested for CDI. The study will collect data on cases/controls (1:3 ratio) identified during the sample collection phase of COMBACTE-CDI.

For each case of confirmed CDI (or other diagnostic criteria), three controls will be randomly selected from the same participating site (i.e. if hospital case, controls will come from the same hospital, if community case, controls will come from the community). Thus initially the controls are only matched on location only, as the cohort is not large enough to enable closer matching. Subsequent further matching (e.g. by age) may be considered depending on final available sample size, but this would reduce the overall pool of controls substantially.

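### The SAP gives outcomes only unadjusted tests and defines no adjusted mortality comparison; read literally, section 7.3 also lets post-index outcomes be selected as risk factors

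*SAP*

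**What the plan says.** **Protocol.** The primary measure for the outcomes study (section 3.2.2) is unadjusted: "Crude mortality at 30 days and 6 months after the sample was taken will be compared between case and controls". Section 3.2.7 adds attributable mortality without naming a method: "Comparisons will be made between recurrence/Morbidity/Mortality (crude and attributable) rates in different healthcare settings and countries".

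**SAP objective.** Section 2.5 puts outcomes first: "Determine the outcomes of cases (of each classification) vs controls, and compare between countries and hospital vs community cases".

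**SAP method for outcomes.** Section 7.2: "Univariate analysis will be used to assess outcomes and risk factors". The tools are the t-test, the chi-squared or Fisher test, and risk or odds ratios. Section 7.2 refers to Appendix 1 for the list of variables.

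**SAP regression.** Section 7.3 specifies one model: unconditional logistic regression with case/control status as the dependent variable. Every variable from the univariate list is a candidate. Selection is forward stepwise, the order of entry ranks the risk factors, and the model is fitted separately by age group. No entry threshold is given.

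**Appendix 1.** Block 10, headed as outcomes, holds discharge (10.1, 10.3), admission and readmission (10.2, 10.4, 10.6), death (10.5, 10.7) and whether a death was linked to CDI (10.5.1, 10.7.1). All are tagged for both univariate and multivariate analysis.

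**Matching.** Protocol section 3.2.3 describes age- and gender-matched controls. SAP section 4 relaxes this: "Thus initially the controls are only matched on location only, as the cohort is not large enough to enable closer matching".

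**The concern.** Cases and controls may differ in age and comorbidity, and both affect mortality. With matching on location only, the design does not remove those differences, and the outcome analysis in 7.2 does not either. A crude excess of deaths among cases could then be read as an effect of CDI when part or all of it is age.

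The only place where adjustment could occur is 7.3, and that model runs the other way: death would be a predictor of being a case. Forward selection forces nothing in, so an adjusted mortality estimate would appear only if death were selected. Events after the index sample could also be ranked as risk factors for CDI, and their presence would change the coefficients of the genuine exposures.

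**Working it through.** **1. Is there an adjusted mortality model?** Reading SAP 7.1 to 7.3 and protocol 3.2.7 together:
- 7.1 is descriptive; its age strata apply to tables.
- 7.2 is unadjusted.
- 7.3 has case status as the dependent variable.
- Protocol 3.2.7 names no model.

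No text gives a model with death as the dependent variable, or a covariate set for one.

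**2. Which variables can enter 7.3?** Section 7.3 takes the univariate list, and 7.2 says that list is Appendix 1. On the literal reading, every item there is a candidate. A narrower reading admits only items tagged for both analyses. Items 10.1 to 10.7 pass either way, and so do discharge destination (2.4), help and purchases during CDI (2.7 to 2.9), CDI severity (4.5.1) and escalation of CDI treatment (7.1, 7.2). The literal reading adds later diarrhoea and CDI testing (4.2, 4.3), whether severity was graded (4.5) and isolation for CDI (5.16). All of these follow the index sample or presuppose CDI.

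**3. How large could crude confounding by age be?** The documents give no mortality figure to reproduce, so this is an illustration.

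Inputs from the SAP:
- Table 1: 103 + 71 + 39 = 213 cases and 365 + 147 = 512 controls. These are maxima, before the control exclusions in 4.1.5 and any missing outcomes.
- Section 3, age over 65 in an earlier study: "previously found 65% in cases and 39% in controls".

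Assumed: death risk *lo* up to age 65 and *hi* above it, equal for cases and controls, so CDI has no effect.

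Crude ratio = (0.65·hi + 0.35·lo) / (0.39·hi + 0.61·lo). The false-positive rate is the exact binomial probability that the two-sided 5% chi-squared test rejects at 213 v 512.

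| lo / hi | Cases | Controls | Ratio | False-positive rate |
|---|---|---|---|---|
| 2% / 6% | 4.60% | 3.56% | 1.29 | 11.6% |
| 3% / 9% | 6.90% | 5.34% | 1.29 | 14.1% |
| 2% / 10% | 7.20% | 5.12% | 1.41 | 20.8% |
| 3% / 15% | 10.80% | 7.68% | 1.41 | 28.9% |

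The result depends on the imbalance. At 3% / 15% with 39% of controls over 65, imbalances of 5, 10 and 20 points give ratios of 1.08, 1.16 and 1.31 and rates of 6.3%, 9.3% and 19.9%. For 5 points: (0.44·15 + 0.56·3) / 7.68 = 8.28 / 7.68 = 1.08.

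**4. Do these rates carry over to 7.3?** No, because 7.3 is fitted within age groups. Under the same split, the older group is 0.65·213 ≈ 138 cases v 0.39·512 ≈ 200 controls, and the false-positive rate there is about 5%. For the younger patients taken as one group (75 v 312) it is about 4%. Suppose, within 65+, that 30% of cases and 20% of controls were 85 or older, with *r* times the mortality of the rest. The ratio is (0.7 + 0.3r) / (0.8 + 0.2r), which is 1.08 for r = 2 and 1.14 for r = 3, with false-positive rates of 6% to 9% at 15% control mortality.

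**5. What could an adjusted model deliver?** Expected deaths at 2% / 6%: 213·0.0460 + 512·0.0356 = 9.8 + 18.2 = 28. At 3% / 15%: 213·0.1080 + 512·0.0768 = 23.0 + 39.3 = 62. In 2,000 simulated studies per setting with no CDI effect and over-65 forced in, the adjusted test rejected in 4.5% and 5.7%, with odds ratios of 1.01 and 1.00. The 95% interval ran from the odds ratio divided by 2.29 (28 deaths) or 1.76 (62 deaths) to the odds ratio times the same factor.

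**The case against.** **The protocol asks for crude mortality, and 7.2 provides it.** This stands. A reader might infer that the primary measure is not delivered; it is. The gap concerns attributable mortality and what SAP objective 1 can be used to conclude. Protocol 3.2.7 mentions attributable rates for comparisons between settings and countries, and items 10.5.1 and 10.7.1 offer one route through recorded cause. Neither is an adjusted comparison of cases with controls.

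**The 7.3 problem is drafting, not intent.** Probably so. Section 7.3 says that it is about risk factors, the partial list in 6.2 contains no outcomes, and Appendix 1 sets block 10 apart. The multivariate tag there may signal an intended outcome model. A reader might infer that the sponsor means to use death as a predictor of CDI; the documents do not show that. But the intended model is not written down, and no sentence excludes the outcomes.

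**Two further inferences are not supported.** The cost analysis in protocol 3.5.7 covers "productivity losses due to illness related disability and death before retirement age". It does not say that the case v control mortality ratio is its input, and the confounding shown arises from the over-65 share, not among younger patients. The SAP's general aim, "Identify and quantify the direct and long-term burden of CDI on healthcare systems", does not promise adjusted attributable mortality.

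**How often 7.3 would report a death estimate is unknown.** With death as the only candidate and entry at p<0.05, both assumed, a true odds ratio of 1.5 in the 65+ group would be retained in 17% to 30% of studies. The real procedure has many candidates and no stated threshold, so this is illustrative and does not describe it.

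**The magnitudes rest on assumptions.** This also stands. The death risks are assumed and not tied to 30 days or 6 months, and the age split comes from another study. With a small imbalance the crude test is close to nominal.

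**Conclusion.** The point holds in a limited form. The crude mortality comparison is specified. An adjusted comparison of 30-day or 6-month death between cases and controls is not, and matching on location only does not replace it. Section 7.3 as literally written permits post-index and CDI-dependent items to be selected and ranked as risk factors. This is most likely a slip, but it should be corrected before analysis.

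If the earlier study's age split recurs, and under-65/over-65 death risks lie between 2%/6% and 3%/15%, age alone would give a crude ratio of 1.29 to 1.41 and a false-positive rate of 12% to 29% at the maximum sample. With a 5-point imbalance the figures are 1.08 and 6%. They apply to the crude test in 7.2 and not to the age-banded model in 7.3.

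**What to change.** **(a) Add an outcome model to the SAP and keep the crude rates.** For death within 30 days (item 10.5), and for death by 6 months (10.5 or 10.7), prespecify one logistic regression each:
- death as the dependent variable and case status as the exposure;
- age (continuous), sex, hospital or community setting, and the comorbidity index already planned in 6.2, all forced in;
- no post-index covariates;
- one fit across age bands, reported whatever its p-value.

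If deaths are few, reduce the covariates to age and setting. The SAP should fix that threshold in advance, since the documents give none. Report estimates for the three diagnostic classes as imprecise.

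**(b) Restrict 7.3.** Limit candidate predictors of case status to exposures that precede the index sample. Exclude items 10.1 to 10.7 and every other post-index or CDI-dependent item, for example 2.4, 2.7 to 2.9, 4.2, 4.3, 4.5, 4.5.1, 5.16, 7.1 and 7.2. Change the Appendix 1 tags to match.

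**Cost.** SAP wording and a little more analysis; the data are already collected. Precision is limited: with about 28 to 62 deaths under the assumed risks, the 95% interval is roughly the odds ratio divided and multiplied by 2.3 to 1.8 with age alone forced in, and slightly wider with the full covariate set.
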